1. INTRODUCTION

The purpose of this document is to provide a description of the statistical methods and procedures to be implemented for the analysis of data from D133HC00003 study. This document is based on protocol version 4.1 Dated 12-Oct-2022.

Document Title:	Document ID:	BP04-01
Statistical Analysis Dlan	Version Number:	3.1
Statistical Analysis Plan	Effective Date:	25-Nov-2021

The statistical planning and conduct of analysis of the data from this study will follow the principles defined in relevant ICH-E9 guidelines. Any change from the planned analysis as described in the protocol, are detailed here, and any differences described here supersede the analysis as presented in the protocol.

2. Study Objective and Design

2.1 Study Objective

2.1.1 Primary Objective

To assess the safety of durvalumab among locally advanced unresectable non-small cell lung carcinoma in Indian patients

2.1.2 Secondary Objective

Not Applicable

2.2 Study Description

2.2.1 Study Design

This is a Phase IV, open-label, single arm, multi-center, prospective study to be conducted in India. Two cohorts of patients will be included in the current study patients with locally advanced, unresectable NSCLC whose disease has not progressed following platinum-based chemoradiation therapy (N= 100). Potential patients will undergo eligibility determination within 7 days prior to first dose. Patients who meet the protocol-defined inclusion/exclusion criteria will be prospectively enrolled in a sequential manner at 10 centres in India. All enrolled patients will be treated with durvalumab administered intravenously over 60 minutes at 10 mg/kg every 2 weeks. The treatment period for this study is 20 weeks, which corresponds to 10 doses of study drug administration. Treatment will continue as long as clinical benefit is observed for a maximum of 20 weeks or either of the criteria defined in section 7 are met, whichever is earlier. Patients who are observed to continue to receive clinical benefit from durvalumab at end of Week 20 will continue treatment in post-trial phase. Any patient who discontinues treatment with durvalumab before end of Week 20 on study will be followed for 90 days after discontinuation of study drug or until the start of alternate treatment intervention, whichever is earlier. Safety will be evaluated throughout the evaluation phase and during the follow up of patients who discontinue treatment before end of Week 20 by physical exams including vital signs, AE/SAE monitoring, laboratory evaluations and recording of concomitant medications.

Document Title:	Document ID:	BP04-01
Statistical Analysis Plan	Version Number:	3.1
	Effective Date:	25-Nov-2021

2.2.2 Inclusion Criteria

Patients are eligible to be included in the study only if all of the following inclusion criteria and none of the exclusion criteria apply:

- 1. Provision of signed, written and dated informed consent prior to any study specific Procedures
- 2. Male or female aged 18 years or older
- 3. As per local prescribing information and in view of positive benefit-risk assessment, patient prescribed Durvalumab treatment as per independent clinical judgment of treating physician for either treatment for locally advanced, unresectable non-small cell lung carcinoma whose disease has not progressed following platinum-based chemoradiation therapy (N= 100)

2.2.3 Exclusion Criteria

[figure not shown]
- Concurrent enrolment in another clinical study, unless it is an observational (non-interventional) clinical study
 or the follow-up period of an interventional study
- 2. Current or prior use of immunosuppressive medication within 14 days before the first dose of study drug, with the exceptions of intranasal and inhaled corticosteroids or systemic corticosteroids at physiological doses, which are not to exceed 10 mg/day of prednisone, or an equivalent corticosteroid. Systemic steroid administration required to manage toxicities arising from radiation therapy delivered as part of the chemoradiation therapy for locally advanced NSCLC is allowed.
- 3. Prior exposure to any anti-PD-1 or anti-PD-L1 antibody including durvalumab.
- 4. For NSCLC cohort only:
 - a. Mixed small cell and non-small cell lung cancer histology
 - b. Any unresolved toxicity CTCAE > Grade 2 from the prior chemoradiation therapy.
 - c. Patients with ≥Grade 2 pneumonitis from prior chemoradiation therapy
- Active or prior documented autoimmune disease within the past 2 years, inflammatory bowel disease (eg, Crohn's disease, ulcerative colitis), primary immunodeficiency, organ transplant that requires therapeutic immunosuppression, hypersensitivity to study drug or any excipient, leptomeningeal carcinomatosis, tuberculosis.
 - NOTE: Patients with vitiligo, Grave's disease, or psoriasis not requiring systemic treatment (within the past 2 years) are not excluded.
- Female patients who are pregnant, breast-feeding or male or female patients of reproductive potential who
 are not employing an effective method of birth control

Document Title:	Document ID:	BP04-01
Statistical Analysis Dlan	Version Number:	3.1
Statistical Analysis Plan	Effective Date:	25-Nov-2021

Any condition that, in the opinion of the investigator, would interfere with evaluation of the study drug or interpretation of patient safety or study results.

2.2.4 Study Flow chart

Document Title:	Document ID:	BP04-01
Statistical Analysis Plan	Version Number:	3.1
	Effective Date:	25-Nov-2021

2.2.5 Study Plan

Dose		1	2	3	4	5	6	7	8	9	10		
Days (± 3 days of windows period)	-7 to 0	1	15	29	43	57	71	85	99	113	127	141	230
Week (1st day of week)		0	2	4	6	8	10	12	14	16	18	Last day of week 20	
Visit	1	2	3	4	5	6	7	8	9	10	ll	12	13
	Screening Period	Evaluation Phase						Follow-up period					
	Screening Visit				Ev	aluatio	n Visi	(2-11))			End of Evaluation Visit	End of Study Visit
Informed Consent Form	X												
Eligibility Criteria	X	X											
Demography and history of tobacco and alcohol use	X												
Medical and surgical history (including all treatments for NSCLC/mUC)	X									1			
Physical examination	X	X Targeted physical exam (based on symptoms) X				X							
Vital signs (pre and post-infusion vital signs assessments; see Section 6.4.8)		X	X	X	X	X	X	X	X	X	X	X	
Urine Pregnancy Test	X												
Weight		X		X		X		X		X			
World Health Organization performance status	X	X	X	X	X	X	X	X	X	X	X	X	
Concomitant medications	X	X	X	X	X	X	X	X	X	X	X	X	
Disease Characteristics Assessment		X			X			X			X	X	
Adverse event/serious adverse event assessment		X	X	X	X	X	X	X	X	X	X	X	X
Electrocardiogram (before dosing of IP)		X				X				X			
Haematology		X	X	X	X	X	X	X	X	X	X	X	
Serum chemistry (LFT, RFT, Electrolytes)		X	X	X	X	X	X	X	X	X	X	X	
Urine Routine and microscopy		X	X	X	X	X	X	X	X	X	X	X	
Thyroid function tests (TSH, T3 and T4) ^a		X				X				X		X	
IP Administration		X	X	X	X	X	X	X	X	X	X	1	

a. Except screening visit, free T3 and free T4 will only be measured if TSH is abnormal or if there is clinical suspicion of an AE related to the endocrine system.

Proprietary	and	Confide	ntial	Document

Document Title:	Document ID:	BP04-01
Statistical Analysis Dlan	Version Number:	3.1
Statistical Analysis Plan	Effective Date:	25-Nov-2021

2.3 Randomization

Not Applicable

2.4 Blinding and Un-Blinding

Not Applicable

2.5 Interim Analysis

No interim analyses is planned for this study.

3. Population Analysis Set

3.1 Enrolled Analysis Set

The enrolled population is defined as all screened patients who provided written informed consent at screening assessment, satisfied all the eligibility criteria and enrolled into the study.

3.2 Safety Analysis Set

All the patients who are enrolled into the study and received at least one dose of investigational product as an IV infusion.

4. Sample Size and Power Calculations

The primary endpoint of the trial is to demonstrate the safety profile of durvalumab in routine clinical practice as assessed by the incidence of Adverse Events (AEs) (Serious and Non-serious AEs) observed during trial. Based on the Durvalumab historic data, estimated proportion of 31% for Adverse Events prevalence rate. With a sample size of 83, would be able to achieve the 10% precision of the estimates with the 95% level of confidence. Approximately 120 participants will be screened to achieve around 100 participants enrolled in the study.

Scenario#	estimated proportion	Precision	Confidence level	Required sample size
1	31%	.15	95%	37
2	31%	.14	95%	42
3	31%	.13	95%	49
4	31%	.12	95%	58
5	31%	.11	95%	68
6	31%	.10	95%	83

Proprietary and Confidential Document	Page 11 of 77

Document Title:	Document ID:	BP04-01
Statistical Analysis Plan	Version Number:	3.1
	Effective Date:	25-Nov-2021

5. Patient Characteristics and Study Conduct Summaries

5.1 General Considerations

Statistical Analysis will be performed using SAS (version 9.4 or higher) software (SAS Institute Inc USA). Categorical variables will be summarized with the frequency, percentage of Patients in each category. Continuous variables will be summarized descriptively with the number of Patients, mean, standard deviation, median, minimum and maximum values.

5.2 Decimal Point

Unless otherwise noted, means, median, will be presented to one decimal place more than the measured value, the same decimal as the measured value, percentages and 95% confidence intervals will be presented to two decimal places and p-value will be presented to three decimal place. Percentages after zero counts will not be displayed and percentages equating to 100% will be presented as 100%, without any decimal places.

5.3 Disposition of Patients

Patient disposition table will be based on all Enrolled Analysis Set who consented to participate in the study. The following summaries will be included in the disposition table: total number of Patient Enrolled in the study, total number of Patients screened in the study, number of Patients who failed screening, number and percentage of Patients who completed the study and number and percentage of Patients who discontinued from the study with reason for discontinuation.

5.4 Demographic and Baseline Characteristics

Demographic and baseline characteristics will be summarized based on the Enrolled Analysis Set.

Descriptive summaries will be provided for the demographic and baseline characteristics. Demographic characteristics and baseline characteristics such as age, Gender and Weight, etc. will be summarized and tabulated for Enrolled Analysis Set.

All the continuous variables will be summarized by n, mean, standard deviation, median, minimum and maximum values. All the categorical variables will be summarized as frequency, percentage of Patients.

5.5 Medical/Surgical History

Medical History will be summarized based on the Enrolled Population.

Descriptive summaries will be provided for the Medical/Surgical History.

All the continuous variables will be summarized by n, mean, standard deviation, minimum, median and maximum values. All the categorical variables will be summarized as frequency, percentage of Patients.

Document Title:	Document ID:	BP04-01
Statistical Analysis Plan	Version Number:	3.1
	Effective Date:	25-Nov-2021

5.6 Radiation Treatment

Radiation Treatment will be summarized based on the Enrolled Population.

Descriptive summaries will be provided for the Radiation Treatment.

All the continuous variables will be summarized by n, mean, standard deviation, minimum, median and maximum values. All the categorical variables will be summarized as frequency, percentage of Patients.

6. Endpoints Analysis Strategy

6.1 Endpoints Analysis

6.1.1 Primary Endpoint

Adverse Events (AEs), Serious Adverse Events (SAEs), and AEs of Special Interest (AESI) including interstitial lung disease/pneumonitis-like events, and on-study deaths.

6.1.2 Secondary Endpoint

Not Applicable

6.2 Efficacy Hypothesis

There is no statistical hypothesis to be tested in this study.

6.3 Statistical Methods for Efficacy Analysis

Statistical Analysis will be performed using SAS (version 9.4 or higher) software (SAS Institute Inc USA). Categorical variables will be summarized with the frequency and percentage of Patients in each category. Continuous variables will be summarized descriptively with the number of Patients, mean, standard deviation, minimum, median and maximum values.

6.3.1 Primary Endpoint Analysis

The primary analysis for primary endpoint will be based on Safety Analysis Set.

Primary Endpoint evaluations will include Adverse Events (AEs), Serious Adverse Events (SAEs), Adverse Events of Special Interest (AESI) including interstitial lung disease/pneumonitis-like events and on study Deaths.

Adverse Events (AEs), Serious Adverse Events (SAEs), Adverse Events of Special Interest (AESI) including interstitial lung disease/pneumonitis-like events and on study Deaths will be summarized using Frequency, Percentages.

Physical Examination will include General Appearance, Respiratory system, Cardiovascular system, Abdomen, Skin, Heent, Neck, Lymph node, Thyroid, Musculo-skeletal system, Genital/Rectal and Neurological System. Physical Examination will be summarized based on the Safety Analysis Set.

Descriptive summaries will be provided for the Physical Examination.

Document Title:	Document ID:	BP04-01
Statistical Analysis Plan	Version Number:	3.1
	Effective Date:	25-Nov-2021

All the continuous variables will be summarized by n, mean, standard deviation, minimum, median and maximum values. All the categorical variables will be summarized as frequency, percentage.

Vital Signs will include Pulse rate, Respiratory rate, Systolic Blood Pressure, Diastolic Blood Pressure, Oxygen Saturation and Temperature. Vital Signs will be summarized based on the Safety Analysis Set.

Vital Signs will be summarised by number of observations, arithmetic mean, SD, median, minimum and maximum values.

12-Lead Electrocardiogram will include Heart rate, QRS, PR, RR, QT and QTcF. 12-Lead Electrocardiogram will be summarized based on the Safety Analysis Set.

12-Lead Electrocardiogram will be summarised by number of observations, arithmetic mean, SD, median, minimum and maximum values.

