This is a Phase IV, open-label, single arm, multi-center, prospective study to be conducted in India. Two cohorts of patients will be included in the current study patients with locally advanced, unresectable NSCLC whose disease has not progressed following platinum-based chemoradiation therapy (N= 100). Potential patients will undergo eligibility determination within 7 days prior to first dose. Patients who meet the protocol-defined inclusion/exclusion criteria will be prospectively enrolled in a sequential manner at 10 centres in India. All enrolled patients will be treated with durvalumab administered intravenously over 60 minutes at 10 mg/kg every 2 weeks. The treatment period for this study is 20 weeks, which corresponds to 10 doses of study drug administration. Treatment will continue as long as clinical benefit is observed for a maximum of 20 weeks or either of the criteria defined in section 7 are met, whichever is earlier. Patients who are observed to continue to receive clinical benefit from durvalumab at end of Week 20 (as defined in SoA) will continue treatment in post-trial phase (defined in section 6.7). Any patient who discontinues treatment with durvalumab before end of Week 20 on study will be followed for 90 days after discontinuation of study drug or until the start of alternate treatment intervention, whichever is earlier.

Safety will be evaluated throughout the evaluation phase and during the follow up of patients who discontinue treatment before end of Week 20 by physical exams including vital signs, AE/SAE monitoring, laboratory evaluations and recording of concomitant medications.

Screening Phase (Visit 1)

Patients, or their legally acceptable representative, will provide written informed consent before any trial-specific procedures are performed. During the Screening Phase, eligibility criteria will be reviewed and a complete clinical evaluation will be performed as specified in the Time and Event Schedule. Screening procedures will be performed 7 days before first dose (week 0, day 1). All baseline disease characteristics will be captured based evaluation performed as a part of routine clinical practice. The documented tests that are required before consideration of patient for durvalumab treatment based on the local prescribing information by investigator must have been performed 28 days before first dose (week 0, Day 1).

Evaluation Phase (Visit 2 To 11)

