Data will be summarized using descriptive statistics. Continuous variables will be summarized using the number of observations, mean, SD, median, and range as appropriate. Categorical values will be summarized using the number of observations and percentages as appropriate.

The safety analysis population will include all patients who sign the ICF and receive at least one dose of durvalumab.

Adverse Events (both in terms of MedDRA preferred terms and CTCAE grade) will be listed individually by patient. Any AE occurring before treatment with durvalumab will be included in the data listings but will not be included in the summary tables of AEs.

[figure not shown]
Any AE occurring within 90 days of discontinuation of investigational product (ie, the last dose of durvalumab) will be included in the AE summaries. Any events in this period that occur after a patient has received further therapy for cancer (following discontinuation of durvalumab) will be flagged in the data listings.

The study is designed in accordance with the Health Authority requirements in India. It is intended to provide information regarding the safety profile for patients in India and will contribute additional information to the overall safety profile of durvalumab. Due to the small sample size, this study should not be directly compared to the data from any other country.

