3. OBJECTIVES AND ENDPOINTS

Table: 2 Study objectives

Primary Objective:	Endpoint/Variable:
To assess the safety of durvalumab among locally advanced unresectable NSCLC	Number, frequency and proportion of patients with adverse events (AEs), serious adverse events (SAEs) and AEs of special interest (AESI) including interstitial lung disease/pneumonitis-like events, and on-study deaths.

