4.2 Scientific rationale for study design

Justification for Study duration:

In the combined safety database with Durvalumab monotherapy, the median time to onset of select adverse events is summarised in the Table below. The current phase IV study includes a

treatment phase of 141 days (20 weeks) which would enable us to detect the incidence of adverse events in eligible Indian patient population.

Table 3: Median time to onset of Immune-mediated Adverse Events

S. No.	Immune-mediated adverse event	Median time to onset (days)
1	Pneumonitis	55
2	Hepatitis	70
3	Diarrhoea/colitis	74
4	Hypothyroidism	85
5	Immune mediated nephritis	91
6	Dermatitis	36
7	Hyperthyroidism	41

Immune-Mediated Pneumonitis

Immune-mediated pneumonitis or interstitial lung disease, defined as requiring use of systemic corticosteroids and with no clear alternate etiology, occurred in patients receiving Durvalumab. Patients should be monitored for signs and symptoms of pneumonitis. Patients with suspected pneumonitis should be evaluated with radiographic imaging and managed as recommended by local guidelines.

Radiation pneumonitis is frequently observed in patients receiving radiation therapy to the lung and the clinical presentation of pneumonitis and radiation pneumonitis is very similar. In the PACIFIC Study, in patients who had completed treatment with concurrent chemoradiation within 1 to 42 days prior to initiation of the trial, pneumonitis including both immune-mediated pneumonitis and radiation pneumonitis, occurred in patients receiving Durvalumab. Pneumonitis or radiation pneumonitis occurred in 161 (33.9%) patients in the Durvalumab -treated group and 58 (24.8%) in the placebo group; including Grade 3 in 16 (3.4%) patients on Durvalumab vs. 7 (3.0%) patients on placebo and Grade 5 in 5 (1.1%) patients on Durvalumab vs. 4 (1.7%) patients on placebo. The median time to onset in the Durvalumab -treated group was 55 days (range: 1-406 days) vs. 55 days (range: 1-255 days) in the placebo group.

Refer to section Appendix D for recommended treatment modifications and management of immune-mediated adverse reactions.

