4 = Completely disabled. Cannot carry on any self-care. Totally confined to bed or chair	xx (xx.xx)
5 = Dead	xx (xx.xx)
Patients performance grade changed, since last visit	
Yes	xx (xx.xx)
No	xx (xx.xx)

- The Capital "N" in the column header represents the total number of patients in Safety Analysis Set.
- The small "n" in summary statistic represents the total number of patients in the row category.
- Percentages are based on total number of patients in Safety Analysis Set.
- Programmer Note: Visit x- Visit 2 up to Visit 13.
- Source: Listing 16.1.10
- Table Name: xxxxx

Document Title:	Document ID:	BP04-01
Statistical Analysis Plan	Version Number:	
Statistical Analysis Plan	Effective Date:	

Table 14.2.1.1 Adverse Events (Safety Analysis Set)

	Durvalumab
	(N=xxx)
	n (%) E
Any Adverse Event	xx (xx.xx) xx
Any Serious Adverse Event	xx (xx.xx) xx
Any Treatment Emergent Adverse Event	xx (xx.xx) xx
Any Serious Treatment Emergent Adverse Event	xx (xx.xx) xx
Treatment Emergent Adverse Event related to IMP	xx (xx.xx) xx
Treatment Emergent Adverse Event leading to IMP discontinuation	xx (xx.xx) xx
Treatment Emergent Adverse Event leading to Death	xx (xx.xx) xx

- The capital "N" in the column header represents the total number of patients in Safety Analysis Set.
- The small "n' in summary represents the number of patients in row category.
- TEAE are those adverse events which occurred after first dose of study medication.
- Note: Adverse events were coded using MedDRA version xx.x
- If a Patient has multiple occurrences of an AE, the Patient is presented only once in the respective patient count column (n)
 for the corresponding AE. Events are counted each time in the event (E)
- Source: Listing 16.3.1.1 and Listing 16.3.1.2

Document Title:	Document ID:	BP04-01
Statistical Analysis Plan	Version Number:	3.1 25-Nov-2021
Statistical Analysis Plan	Effective Date:	

Table 14.2.1.2 Summary of Adverse Event (Safety Analysis Set)

	Durvalumab (N=xxx) n (%) E
Any Adverse Event reported	xx (xx.xx) xx
Severity as per CTCAE grade	
Mild	xx (xx.xx) xx
Moderate	xx (xx.xx) xx
Severe	xx (xx.xx) xx
Life Threatening	xx (xx.xx) xx
Death	xx (xx.xx) xx
Action Taken to Study Drug	
No Change in IP	xx (xx.xx) xx
IP Temporarily Interrupted	xx (xx.xx) xx
IP Permanently Discontinued	xx (xx.xx) xx
Other	xx (xx.xx) xx
Treatment Given	
Yes	xx (xx.xx) xx
No	xx (xx.xx) xx
Relationship with Study Drug	. ,
Related	xx (xx.xx) xx
Not Related	xx (xx.xx) xx
Outcome	
Resolved	xx (xx.xx) xx

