Recovered/ Resolved with Sequelae	xx (xx.xx) xx
Recovering/ Resolving	xx (xx.xx) xx
Not Recovered/ Not Resolved	xx (xx.xx) xx
Fatal/ result in death	xx (xx.xx) xx
Unknown	xx (xx.xx) xx
Serious Adverse Event	
Yes	xx (xx.xx) xx
No	xx (xx.xx) xx
Seriousness Criteria	,
Death	xx (xx.xx) xx
Life-threatening	xx (xx.xx) xx
Inpatient hospitalization or prolongation of existing hospitalization	xx (xx.xx) xx
Proprietary and Confidential Document	Page 29 of 77

Document Title:	Document ID:	BP04-01
Sandindinal Amelusia Plan	Version Number:	3.1
Statistical Analysis Plan	Effective Date:	25-Nov-2021

Persistent or significant disability/ incapacity	xx (xx.xx) xx
Congenital anomaly/Birth Defect	xx (xx.xx) xx
Important medical events	xx (xx.xx) xx
Therapy Discontinued	
Yes	xx (xx.xx) xx
No	xx (xx.xx) xx

- The Capital "N" in the column header represents the total number Safety Analysis Set.
- The small "n" represents the total number of patients in the row category.
- All Percentages rows are based on number of Safety Analysis Set.
- TEAE = treatment-emergent adverse event; E = number of TEAE
- All Percentages are based on the total number of Safety Analysis Set.
- Source: Listing 16.3.1.1 and Listing 16.3.1.2

Table 14.2.1.3 Summary of Treatment Emergent Adverse Events by System Organ Class and Preferred Term (Safety Analysis Set)

	Durvalumab (N=xxx)
	n (%) E
Any TEAE	xx (xx.xx) xx
System Organ Class 1	xx (xx.xx) xx
Preferred Term 1	xx (xx.xx) xx
Preferred Term 2	xx (xx.xx) xx
System Organ Class 2	xx (xx.xx) xx
Preferred Term 1	xx (xx.xx) xx
Preferred Term 2	xx (xx.xx) xx

- TEAE = treatment-emergent adverse event; N = number of Patients in the Safety Analysis Set; n = number of Patients with TEAE; E = number of TEAE
- All Percentages are based on the number of patients in Safety Analysis Set.
- System Organ Class and Preferred term are coded using MedDRA version xx.x
- System Organ classes and preferred term are sorted by descending frequency. Preferred terms are sorted by descending frequency within system organ class.
- Source: Listing 16.3.1.1 and Listing 16.3.1.2

Document Title:	Document ID:	BP04-01
Statistical Applicate Plan	Version Number:	per: 3.1
Statistical Analysis Plan	Effective Date:	25-Nov-2021

Table 14.2.1.4 Summary of Serious Treatment Emergent Adverse Events by System Organ Class and Preferred Term (Safety Analysis Set)

	Durvalumab (N=xxx)
	n (%) E
Any Serious TEAE	xx (xx.xx) xx
System Organ Class 1	xx (xx.xx) xx
Preferred Term 1	xx (xx.xx) xx

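### The primary adverse event percentages have no single time horizon: observation time differs between patients by design, and the documents give several AE windows

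*SAP*

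**What the plan says.** **Analysis.** SAP 6.3.1 has all components of the primary endpoint "summarized using Frequency, Percentages". The mock tables in SAP Section 8 show n (%) and an event count E that is not divided by time. The footnote to Table 14.2.1.3 reads "All Percentages are based on the number of patients in Safety Analysis Set". No patient-time, rate, time-to-event summary or summary of follow-up duration is planned.

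**Length of observation.** Under the overall design in Protocol 1.2, a patient who stops early "will be followed for 90 days after discontinuation of study drug or until the start of alternate treatment intervention, whichever is earlier". Protocol 7.1 says the same. Under 7.2, withdrawal from the study ends observation that day.

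**AE window.** Four places give four answers:
- The Schedule of Activities and the follow-up paragraph of Protocol 1.2 schedule a contact for every patient 90 days after the End-of-Evaluation visit, about Day 230.
- The statistical paragraph of Protocol 1.2 says "Any AE occurring within 90 days of discontinuation of investigational product (ie, the last dose of durvalumab) will be included in the AE summaries".
- Protocol 8.2.2 states post-treatment AE collection only for patients who stop before 20 weeks.
- The footnote to SAP Table 14.2.1.1 says "TEAE are those adverse events which occurred after first dose of study medication", which gives a start and no end.

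**Duration.** Protocol 4.2 justifies a 141-day treatment phase, "which would enable us to detect the incidence of adverse events in eligible Indian patient population", by the median onset times in Table 3 (36 to 91 days).

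**The concern.** A crude percentage estimates the risk to a stated day only if every patient is observed to that day, or has died before it. Here a patient who stops after the first dose is observed to Day 91 at most (1 + 90), and for less time if new therapy starts. A patient who completes 10 doses has three possible ends: Day 141 under 8.2.2, Day 217 under the 90-days-after-last-dose rule (127 + 90), or about Day 230 under the Schedule of Activities. If that patient continues durvalumab under post-trial access (6.7), the last dose has not yet been given, and the 90-day rule sets no end within the study.

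Adverse events and progression are among the listed reasons for stopping (7.1), so shorter observation may be related to risk. Protocol 1.2 and SAP Section 4 both call the primary quantity an incidence. These percentages are the study's main product for the Indian health authority, whose readers will need to know to which day each percentage refers.

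**Working it through.** **1. The plan's own figure.** The only numerical target is precision. With p = 0.31 and d = 0.10, n = 1.96² × 0.31 × 0.69 / 0.10² = 82.17, rounded up to 83. The other five rows of the scenario table also reproduce. At N = 100 the 95% half-width is 1.96 × √(0.31 × 0.69 / 100) = 9.1 points, which is the yardstick for the errors below.

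**2. Model.** From Protocol 4.2: pneumonitis or radiation pneumonitis in 33.9% of durvalumab patients, median onset 55 days. Assumed: 33.9% is the eventual risk; onset is exponential, so the share of onsets by day t is F(t) = 1 − 2^(−t/55); a share s of patients (10-40%) stops early, uniformly over Days 1-141; stopping is independent of risk.

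- F(141) = 0.831, so Day-141 risk = 33.9 × 0.831 = 28.2%.
- F(230) = 0.945, so Day-230 risk = 33.9 × 0.945 = 32.0%.

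Averaged over stop days u from 1 to 141:
- nothing observed after stopping: mean F(u) = 0.536
- observed to u + 90, events counted no later than Day 141: 0.807
- observed to u + 90: 0.851

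**3. Error of the crude percentage** = 33.9 × s × (mean F for early stoppers − F at the target day).

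| Window | Target | Calculation | s = 10% | s = 40% |
|---|---|---|---|---|
| Full 90-day follow-up, events to Day 141 | Day 141 | 33.9 × s × (0.807 − 0.831) | −0.1 | −0.3 |
| 8.2.2: completers to Day 141, early stoppers to stop + 90 | Day 141 | 33.9 × s × (0.851 − 0.831) | +0.1 | +0.3 |
| Completers to Day 230, early stoppers to stop + 90 | Day 230 | 33.9 × s × (0.851 − 0.945) | −0.3 | −1.3 |
| Nothing observed after stopping | Day 141 | 33.9 × s × (0.536 − 0.831) | −1.0 | −4.0 |
| Nothing observed after stopping | Day 230 | 33.9 × s × (0.536 − 0.945) | −1.4 | −5.5 |

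Follow-up cut short by new therapy or withdrawal lies between the full-follow-up and no-follow-up rows. The second row is positive because, under 8.2.2, anyone stopping after Day 51 (51 + 90 = 141) is observed longer than a completer.

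**4. The sign depends on the horizon.** Take an extreme case: 30% of patients stop after dose 1 and are followed to Day 91, and the rest are observed to Day 230. The crude figure is 0.7 × 32.03 + 0.3 × 33.9 × (1 − 2^(−91/55)) = 22.42 + 6.94 = 29.4%. This is 2.7 points below Day-230 risk and 1.2 points above Day-141 risk.

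**5. Sensitivity.** Fix the true risk at 31% at the target day and let the median onset be 55 or 91 days. With full follow-up the crude figure is at most 0.5 point low at Day 141 and 0.3-2.0 points low at Day 230. Under the 8.2.2 window it is 0.1-0.6 point high. With nothing observed after stopping it is 1.1-5.1 points low at Day 141 and up to 6.6 points low at Day 230 (24.4% against 31%).

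**6. The duration statement.** All seven medians in Table 3 lie below 141 days, so at least half of the onsets in the source data fall within 20 weeks. With exponential onset the share by Day 141 runs from 65.8% (nephritis, median 91) to 93.4% (dermatitis, median 36). Lognormal onset (sigma 0.8 or 1.2) gives 64-96%. The cited pneumonitis onset range extends to 406 days.

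**The case against.** The strongest reply is that the plan delivers what it promises. Protocol Section 3 defines the endpoint as numbers and proportions of patients. The study is single-arm and descriptive with no hypothesis test, so unequal follow-up cannot bias a comparison between arms. Doses received and reasons for discontinuation are tabulated. Protocol 1.2 asks for the telephone visit before subsequent treatment starts, and 7.2 seeks vital status for all patients at study end. A patient who stops because of an AE already counts in the any-AE proportion, and where observation ends in death the crude proportion already treats death as a competing event. With the planned follow-up obtained, the error is small beside a 9.1-point half-width.

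Most of this stands, and it is why n (%) should remain the primary summary. It does not supply a horizon. The 90-day rule in Protocol 1.2 conflicts with 8.2.2 and is unclear for patients who continue on post-trial drug. The 90 days may also be cut short by new therapy, although the same synopsis plans to flag events after such therapy in the listings. A patient who stops for one AE or for progression can still be under-observed for another event, such as pneumonitis.

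A reader might go further and infer that incidence is understated. The documents do not support that: the sign changes with the window and the target day, and no early-stopping rate is given. A reader might also infer that the statement in Protocol 4.2 fails. That goes too far, because every listed median falls within 141 days. What is missing there is the words 20-week.

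**Conclusion.** The point holds as one of definition and reporting. The primary percentages pool patients observed for different lengths of time under windows that the documents do not agree on, and no planned output fixes a day. The likely error is a fraction of a point at Day 141, and 0.3-1.3 points at Day 230, if the 90-day follow-up is largely obtained. It approaches 4.0 points (Day 141) or 5.5 points (Day 230) only if 40% of patients stop early and none is observed afterwards. These figures rest on assumed early stopping of 10-40%, uniform stop times, exponential onset with median 55 days, 33.9% taken as eventual risk, and stopping unrelated to risk. None of these assumptions is in the documents except the 55 days and the 33.9%, and the latter is reported there as a plain proportion. Protocol 4.2 supports a claim about 20-week incidence, not about incidence without a time limit. The change is worth making because it is cheap; the planned n (%) remains valid as a description.

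**What to change.** 1. Keep n (%) as the protocol-defined endpoint.
2. Reconcile the Schedule of Activities and the follow-up and statistical paragraphs of Protocol 1.2, Protocol 8.2.2 and the TEAE footnote to SAP Table 14.2.1.1 to one AE window for analysis. State how it applies to patients who continue on post-trial drug or start new therapy.
3. Add to SAP 6.3.1 and Table 14.2.1.1, for any TEAE, serious TEAE and pneumonitis/other AESI (the table has no AESI row at present): total patient-time at risk, and cumulative incidence at Day 141 with 95% CI, censoring at end of observation and treating death as a competing event. Day 141 is a horizon that each of the protocol's windows reaches for a completer.
4. Reword Protocol 4.2 to say that the design estimates 20-week incidence.

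The dates needed are already planned for listing: infusions (16.1.4.1), AE onset (16.3.1.2) and study completion or discontinuation (16.1.1.3). The cost is a few derived variables, some programming and a slightly wider interval. The estimate may move up or down relative to the crude percentage.
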